## VIII. POTENTIAL RISKS AND BENEFITS

Potential risks associated with any vaginal delivery regardless of study participation:

- Maternal risks including infection and all risks associated with vaginal delivery including but not limited to hemorrhage, laceration, sepsis, and other rare maternal morbidity and mortality
- Neonatal risks associated with vaginal delivery including but not limited to infection, sepsis, water inhalation, umbilical cord avulsion, respiratory distress, low APGAR scores, NICU admission, and rare adverse neonatal morbidity and mortality including neonatal death

Potential benefits although unknown:

- Maternal benefits may include improved pain control, fewer obstetric lacerations, increased comfort during labor, increased mobility, and ease of delivery positioning due to increased buoyancy, improved relaxation, a more satisfying birth experience, increased perception of control, decreased cesarean delivery, and an additional option for pain control in a hospital setting in the Milwaukee area.
- Neonatal benefits may include less exposure to maternal pain medication/narcotic use, fewer interventions in labor, fewer instrumental and cesarean deliveries, immediate skin-to-skin contact with improved infant maternal bonding, and fewer NICU admissions.

Waterbirth is considered by ACOG/AAP to be an experimental procedure and, therefore, not all risks and benefits are known. It is considered a beneficial option for low-risk healthy women by the American College of Nurse Midwives and the Royal College of Obstetricians and Gynecologists/Royal College of Midwives. Providers who participate in the study will receive standardized training for waterbirth and will be in compliance with our internal Institutional Review Board research guidelines. Nursing staff will receive training by the study PI and co-investigators.

If our pilot study shows that waterbirth is a reasonable option for low-risk healthy women, we will seek to implement a larger, multi-center trial on the labor and delivery floor at Aurora Sinai Medical Center and at other Advocate Aurora hospitals. Additionally, we seek to publish and disseminate our findings so that other hospitals can adopt our protocols. Lastly, we also seek to model interdisciplinary collaboration between obstetrics, midwifery, and neonatology to offer this service.

## **Appendix A.**

Example/tentative dot.phrases for waterbirth study:

### ***.waterbirthconsent2***

Patient confirms adequate time to review informed consent document

The informed consent was reviewed page by page with the patient. The following were discussed and reviewed with the patient: purpose of study, investigational nature, procedure, follow-up, risks, benefits, alternative therapy, voluntary participation, right to refuse participation without consequences to continued care or access, confidentiality/privacy.

Patient verbalizes understanding and acknowledges all questions have been answered.

Outcome: Patient verbalizes willingness to participate and agrees to participate if all study eligibility criteria are met.

No study related procedures were performed prior to signing the study informed consent. A copy of the signed informed consent was given to the patient and a copy was placed in patient medical record chart.

Subject is enrolled

### ***.waterbirthexclusion***

This participant has been excluded from the waterbirth research study due to \*\*\*. The appropriate study coordinators and study team members have been notified.

### ***.waterbirthlaborprogress [1776244]***

This labor progress note includes standard of care labor assessments, in addition to documentation for hourly water temperatures.

### ***.waterbirthsecondstage***

The subject is now in the second stage of labor. I \*\*\* am comfortable proceeding with the subject on the waterbirth study who was randomized to the waterbirth.

**Appendix B.**

## Waterbirth Hourly Tub Temperature

0700	1900
0800	2000
0900	2100
1000	2200
1100	2300
1200	0000
1300	0100
1400	0200
1500	0300
1600	0400
1700	0500
1800	0600

## **Appendix C.**

### **Waterbirth Tub Protocol**

#### **Tub inflation**

1. First inflate the bottom of the pool, starting with the floor valve, with the electric air pump. Use the appropriate size nipple.
2. Next, inflate the patient seat, using the valve on the seat with the electric air pump. Use the appropriate size nipple. These can be VERY full, like a football. Do not worry about overfilling this part!
3. Next inflate each wrung, starting with the bottom and moving up. You can make it VERY full.

\*Inflating the tub takes approximately 10-15 minutes\*

#### **Tub Cleaning**

1. Dispose of the individual liner and hose
2. Wipe out the tub with Sanitizing-wipes
3. Allow to the tub to COMPLETELY DRY

#### **Tub Deflation**

1. After tub is completely dry, use the electric air pump to deflate it.
2. Start with the top wrung and move down.
3. Deflate the patient seat
4. Deflate the floor
5. Fold tub and place back in the bag

### **Introduction:**

This monitoring plan includes reviews for both data integrity and subject safety. The study PI, co-investigators, Maternal Newborn Quality Committee and the Advocate Aurora Health Care Institutional Review Board will be involved in monitoring activities. These activities will be conducted in accordance to applicable regulations, ICH-GCP and institutional/IRB policies.

Data and safety monitoring activities and the roles of individuals involved are described below. The schedule and scope of each review is outlined as well.

This monitoring plan was prepared based on considerations such as purpose, design, complexity, size, and endpoints of the trial. Monitoring activities will be documented with a brief written report and on a subject monitoring log.

### **Monitoring plan:**

#### *PURPOSE*

The purposes of trial monitoring are to verify that:

- (a) The rights and well-being of human subjects are protected.
- (b) The reported trial data are accurate, complete, and verifiable from source documents.
- (c) The conduct of the trial follows the currently approved protocol/amendment(s) and applicable regulatory requirement(s).

#### *ROLES/REVIEWS*

PI and co-investigators: The Principle investigator and co-investigators will carefully assess and evaluate the first ten subjects and their infants following a completed waterbirth to monitor for any rare adverse outcomes that may or may not have been known prior to study start. As subjects may risk out and become ineligible for waterbirth prior to delivery, outcomes on the first ten subjects and their infants will be evaluated only for subjects who completed a waterbirth.

For all subjects, the Principal Investigator and co-investigators will continue to review all adverse outcomes and will regularly monitor the data to identify trends throughout the study.

The Principal Investigator and co-investigators will be responsible for reporting all adverse events to the IRB and for revising the protocol as needed to maintain safety. Primarily, the Principal Investigator and Manager of Translational Research for AUWMG (co-investigator) are responsible for the IRB submissions, ClinicalTrials.gov registration, safety reporting and other regulatory components of the study.

Maternal Newborn Quality Committee: The Maternal Newborn Quality Committee, an internal hospital committee at Aurora Sinai Medical Center, is involved in monitoring all maternal and neonatal adverse outcomes at the facility.

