### **A. Management of labor in water**

1. Before immersion, ensure that the woman is a candidate for warm water immersion based on inclusion and exclusion criteria
  - a.) The tub should be filled using ordinary tap water without additives (e.g., salt, essential oils, sanitizers).
  - b.) The water temperature should be assessed and documented hourly by nursing.
  - c.) During the first stage of labor in water, the water temperature should never exceed 37.7°C (100°F) and may be adjusted to cooler temperatures per the woman's preference.
2. The woman in labor may enter or leave the water at any point with assistance.
  - a) The woman should be instructed to use proper body mechanics when entering and exiting the tub and do so only with staff or a support person in attendance.
  - b) If complications or changes occur in the maternal or fetal condition that require further assessment or treatment outside of the tub, share this information with the family and assist the woman out of the tub.
3. Positioning for comfort in the tub is dependent on the preferences of the woman and the judgment of the provider in consultation with the woman.
4. Provide hydration in the form of oral liquids or intravenous (IV) fluids as indicated. All IV or saline lock sites should be covered with an occlusive, water-resistant dressing while the woman is in the tub.
5. The well-being of the woman and fetus are assessed and managed in accordance with practice protocols for *any other woman* during labor, including monitoring maternal vital signs, assessing the fetal heart rate and initiating intrauterine resuscitation strategies when indicated (e.g., maternal position changes and IV fluid bolus for fetal heart rate changes or Category II fetal heart rate).

- a.) A waterproof Doppler or waterproof electronic fetal monitoring equipment should be used to assess the fetal heart rate.
- b.) Waterproof electronic fetal monitoring equipment may be used to verify or clarify if an indeterminate fetal heart rate pattern is present, and this can guide management.
- c.) Management of indeterminate fetal heart rate patterns depend on multiple factors. Intrapartum resuscitation techniques such as position change, hydration, and correction of hypotension or tachysystole are instituted as necessary.

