### **E. Complications**

1. As when caring for any woman in labor, the health care professional is responsible for using clinical judgment to respond appropriately when complications arise. If deviations from normal during immersion are observed, the woman should be asked to exit the tub and assisted out of the water for further assessment as necessary to perform standard care assessments and interventions.

A. *Tight nuchal cord:* If a tight nuchal cord cannot be reduced, and the somersault maneuver is ineffective, the woman should be assisted to stand above the water so

the cord can be clamped and cut to facilitate birth out of the water. **Under no circumstances should a nuchal cord be clamped and cut under water.** The woman should remain standing to give birth to the rest of the body and to avoid submersion of the neonate's head after birth. The tub will be drained.

B. *Shoulder dystocia*: If a shoulder dystocia occurs in the tub and cannot be resolved with position change, assist the woman out of the tub to complete the birth. Once the neonate's head is exposed to air, it should not be re-submerged.

C. *Excessive bleeding*: The presence of excessive bleeding into the water should prompt the immediate evaluation of the source. According to Waterbirth International, the water should never be dark enough that the woman is not visible through the water. In the case of excessive bleeding, assist the woman out of the tub for further evaluation. Initiate quantification of blood loss to more accurately assess blood loss volume. Excessive bleeding or blood loss will be determined based on the color of the water in the tub. Obstetricians, midwives, and nursing staff will be taught to evaluate the amount of bleeding prior to the start of the study. There should be minimal bleeding prior to the birth of the baby, and more than minimal bleeding in the first stage of labor should prompt the team to assist the woman out of the water.

D. *Umbilical cord avulsion*: If cord rupture is suspected, the cord should be immediately clamped at the umbilicus and cut. Cord clamps must be readily available. If cord rupture is confirmed, the newborn should be removed from the tub for assessment.

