We will compare baseline characteristics and pre-determined outcomes between patients who are randomized to either waterbirth or land birth. We will compute frequencies, means with 95% confidence intervals, and medians with interquartile ranges, as appropriate per variable type. Differences among the groups will be tested using the Pearson chi-squared test of independence (or Fisher's exact), Student's t-test, or Wilcoxon's rank sum test, respectively. Continuous variables will be assessed for normal distribution. Categorical variables will be assessed for collinearity. Potentially, we will use logistic regression for binary categorical outcomes (e.g., opioid use/anesthetist intervention, maternal tears, vaginal birth versus conversion to cesarean section, etc.) and linear regression for continuous outcomes (e.g., blood loss, time to skin-to-skin contact, etc.). Potentially, we will also perform ordered logistic regression on ordinal outcomes such as satisfaction level and APGAR. All underlying assumptions will be tested for each statistical method used. A one tailed p value lower than 0.05 will be considered statistically significant.

Please note, a data safety monitoring plan has been created for this study and is included in Appendix D. The first ten subjects that are enrolled for a waterbirth will be monitored and reviewed by the study PI, co-investigators, and Maternal Newborn Quality Committee for any rare adverse outcomes. For all subjects, the Principal Investigator and co-investigators will continue to review all adverse outcomes and will regularly monitor the data to identify trends throughout the study.

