#### *DESCRIPTION OF REVIEWS AND REPORTING*

##### Schedule and scope of data integrity reviews (study team):

	Initial Review	Continued Review
Conducted by	PI, co-investigators, and Maternal Newborn Quality Committee	PI, co-investigators, and Maternal Newborn Quality Committee
When will review be conducted	After ten subjects and their infants in the waterbirth arm give birth in the water	Regularly throughout the study
What will be reviewed	100% of all data entered compared to source documents, any paper CRFs, etc.	100% of all data entered compared to source documents, any paper CRFs, etc.
Purpose of review	To monitor for any rare adverse outcomes that may or may not have been known prior to study start for waterbirth	To continue to regularly monitor for any rare adverse outcomes that may or may not have been known prior to study start for waterbirth
Reporting	
A brief written report will be prepared by the Principal Investigator and study co-investigators that will be inclusive of feedback from the Maternal Newborn Quality Committee. This brief written report will be shared with the study team and the Advocate Aurora Health Care Institutional Review Board.
 
Any adverse outcome(s) will be logged on a subject monitoring log.
	
Should the study team deem it necessary, an additional brief written report may be shared.
 
Any adverse outcome(s) will be logged on a subject monitoring log.

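### The initial safety review is defined in two ways, and the narrower definition leaves out harms that bring a woman out of the tub before birth

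*Combined protocol and SAP*

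**What the plan says.** Section VII (Statistical Plan) describes the initial safety review by assignment: "The first ten subjects that are enrolled for a waterbirth will be monitored and reviewed". The data and safety monitoring plan describes it by how the birth ended. Under Roles/Reviews, "outcomes on the first ten subjects and their infants will be evaluated only for subjects who completed a waterbirth", and the reason given is "As subjects may risk out and become ineligible for waterbirth prior to delivery". The schedule table sets the timing as "After ten subjects and their infants in the waterbirth arm give birth in the water" and the purpose as "To monitor for any rare adverse outcomes that may or may not have been known prior to study start for waterbirth".

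The waterbirth protocol (Section V) takes women out of the water when problems arise. Section V.A has a general rule that begins "If complications or changes occur in the maternal or fetal condition that require further assessment or treatment outside of the tub" and ends with the woman being helped out. Section V.E adds specific cases. For shoulder dystocia the text reads "If a shoulder dystocia occurs in the tub and cannot be resolved with position change, assist the woman out of the tub". A tight nuchal cord that cannot be reduced, more than minimal bleeding in the first stage, and loss of consciousness also lead out of the water.

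The initial review ends in a written report that goes to the study team and the IRB. In the continued review a further written report is optional, and the timing is given only as regular.

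**The concern.** Two things look wrong. First, the two sections define different groups of ten, so the team could follow either and claim compliance.

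Second, under the monitoring plan's definition, being counted depends partly on the outcome under review. A woman whose shoulder dystocia is not resolved in the tub, and who gives birth out of it, has not given birth in the water and is not among the ten. The reason given, risking out before delivery, supports leaving out women who never entered the water. It does not support leaving out women who were immersed and then removed for a complication, and the wording does not separate the two.

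At stake is the only review with a fixed trigger and a required summary to the IRB, at the point when the procedure is newest to the unit. It could look more reassuring than the experience of all immersed women would justify.

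**Working it through.** The documents attach no detection probability to the ten-subject review, so there is no stated figure to reproduce. The check has two parts.

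**1. Which events the restricted review can see**

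| Event | Where described | Seen among completed waterbirths? |
|---|---|---|
| Shoulder dystocia unresolved in the tub | V.E | No: "cannot be resolved with position change, assist the woman out of the tub to complete the birth" |
| Tight nuchal cord, cut above the water | V.E | No: the birth is finished out of the water |
| More than minimal first-stage bleeding | V.E | No, unless she returns and gives birth in the water |
| Loss of consciousness before birth | V.E | No |
| Other maternal or fetal change needing care outside the tub | V.A | No, unless she returns |
| Shoulder dystocia resolved by position change | V.E | Yes |
| Cord avulsion, neonatal respiratory problems, infection, NICU admission | V.E, Data Collection, VIII | Yes, after an underwater birth |
| Postpartum bleeding, lacerations | V.C | Yes: assessed in bed after the birth |

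The restriction therefore removes one class of event, the one that ends immersion before birth, and leaves the other intact.

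**2. What that can do to detection (illustration)**

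Let c be the risk of an in-tub complication per immersed woman, and f the share of such cases that lead to exit before birth. Both are assumptions, since the documents give neither. Exits for other reasons are ignored.

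- Ten immersed women: P(at least one case) = 1 − (1 − c)^10.
- Rate left among completed waterbirths: r = c(1 − f)/(1 − cf).
- Ten completed waterbirths: P(at least one case) = 1 − (1 − r)^10.

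At c = 5%, ten immersed women give 1 − 0.95^10 = 40.1%. Among ten completed waterbirths:

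- f = 25%: r = 0.0375/0.9875 = 0.0380, giving 32.1%.
- f = 50%: r = 0.025/0.975 = 0.0256, giving 22.9%.
- f = 75%: r = 0.0125/0.9625 = 0.0130, giving 12.3%.
- f = 100%: r = 0, giving 0%.

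Over a range of assumed risks:

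| c | Ten immersed | f = 25% | f = 50% | f = 75% | f = 100% |
|---|---|---|---|---|---|
| 5% | 40.1% | 32.1% | 22.9% | 12.3% | 0% |
| 10% | 65.1% | 55.1% | 41.8% | 24.0% | 0% |
| 20% | 89.3% | 82.1% | 69.2% | 45.5% | 0% |

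If the trigger stays at ten completed waterbirths but every woman immersed by then is reported, a case is missed only if none occurred. With no other exits, that requires the first ten immersed women all to be free of a case, which has probability (1 − c)^10. The ten-immersed column is then recovered in full, 40.1% at c = 5%.

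**The case against.** The case against has real force.

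- **Other oversight exists.** The monitoring plan requires continuing review of adverse outcomes in all subjects, makes the investigators responsible for reporting all adverse events to the IRB, and notes that a hospital committee monitors maternal and neonatal adverse outcomes across the facility. Data Collection records switches from waterbirth to land birth and the reason. A reader might infer that women removed from the tub escape oversight, or that the ten-birth report is all the IRB receives. The documents do not support that. What these provisions lack is a required summary with a denominator: how many women were immersed, how many left, and why.
- **Much of the signal is kept.** A reader might infer that the review is conditioned on the absence of the very harms it seeks. That is too strong. The neonatal risks that Section I calls the most controversial aspect arise largely at or after an underwater birth, and these remain in view.
- **Ten actual underwater births is a sensible trigger.** Section I treats first-stage immersion as having established safety. Making the first ten tub entrants the denominator could leave few underwater births in the review. This stands, and the fix below keeps the trigger.
- **The 39.4% attrition rate does not measure the gap.** One could compute 10/(1 − 0.394) = 16.5, so about 17 randomised women for ten completions, and infer that about seven tub complications go unreported. But the 39.4% is the rate of risking out of the study, it is not given by arm, and the listed reasons for ineligibility include hepatitis C, gestational age and non-vertex presentation. Many of these women may never have entered the tub.
- **Data on removed women are anticipated.** Section IV stops data collection on women who become ineligible for waterbirth, but it then applies intention to treat to those who remain eligible, and Section III keeps women excluded by the birth attendant in their assigned group. The text is ambiguous, not a clear bar. Still, fever and Category 2 or 3 fetal heart tones are listed reasons for ineligibility. If either arose during immersion, Section IV could be read as ending data collection.

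**Conclusion.** The point holds in a limited form. The two definitions of the initial review conflict and must be reconciled. The narrower one leaves harms that prompt exit before birth out of the only review with a fixed trigger and a required IRB summary. The size cannot be taken from the documents, because they give no rate of tub exit or of in-tub complications. At an assumed 5% risk, the chance of seeing at least one case falls from 40% to 32%, 23% or 12% for exit shares of 25%, 50% or 75%. A reader might infer that detection is about zero, but that follows only if every case leads to exit before birth, which the documents do not say. The illustration also assumes independent women and no exits for other reasons. The loss concerns one summary report and part of the signal, not safety oversight as a whole. The change should be made because it is cheap and improves the first formal look.

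**What to change.** Reconcile Section VII (Statistical Plan), Roles/Reviews and the schedule table to one rule:

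1. Keep ten completed waterbirths as the trigger.
2. Have the initial review and its IRB report cover every water-arm woman who entered the tub up to that point, wherever she gave birth. State the number immersed, the number who left the water, the reasons, and the maternal and newborn outcomes.
3. List women who risked out before immersion separately, so that they do not blur the denominator.
4. State in Section IV that the end of data collection on ineligibility does not apply to safety data for women who entered the tub.

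No clinical rule changes. The cost is an edit to the monitoring plan and protocol wording, plus a few extra chart reviews by the same reviewers.
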